7.1.1.2 Patient demographics and other baseline characteristics

The following patient demographics and baseline characteristics will be collected on the eCRF:

- Demography including date of birth, race and ethnicity
- Height, weight (See [Section 7.2.2.3](#))
- Diagnosis of Primary Myelofibrosis, Post-Polycythemia Vera Myelofibrosis, or Post-Essential thrombocythemia Myelofibrosis
- Myelofibrosis history and prior/concomitant myelofibrosis treatment
- Cytogenetics
- Complete Medical History and current medical conditions
- Prior Myeloproliferative neoplasm directed therapy-medications
- Prior Anti-neoplastic Radiotherapy
- Prior Anti-neoplastic Surgery
- Transfusion history for the last 12 weeks prior to screening
- All other medications and non-drug therapies (including physical therapy and oxygen) administered to the patient within 30 days prior to the first dose of study drug) must be reported on the Concomitant Medications or the Surgical and Medical Procedures eCRFs
- Patient self-rating quality of life questionnaire (EORTC QLQ C-30) (See [Section 7.2.6.1.2](#))
- Biomarker assessments (See [Section 7.2.4](#))

Furthermore the following assessments will be performed to assess the eligibility of the patient:

- Inclusion/Exclusion (see [Section 5.2](#) and [Section 5.3](#))
- Physical Examination (See [Section 7.2.2.1](#))
- Vital signs (See [Section 7.2.2.2](#))
- ECOG performance status (See [Section 7.2.2.4](#))
- Measurement of spleen by palpation (See [Section 7.2.1.1](#))
- Prognostic factors for MF
- Myelofibrosis Symptom Assessment Form
- Bone Marrow Biopsy and aspirate (see [Section 7.2.1.3](#))
- ECG (See [Section 7.2.2.5.7](#))
- Laboratory evaluations (See [Section 7.2.2.5](#))
- Serum pregnancy test (See [Section 7.2.2.5.6](#))

7.1.2 Treatment period

Patients will be treated with LDE225 and INC424 for at least 2 years after the first dose or until death, documented disease progression, initiation of a new MF therapy, intolerable toxicity, withdrawal of consent, discontinuation at the discretion of the investigator, or lost to follow-up, whichever comes first. Patients who complete 2 years of treatment and are deriving clinical benefit in the opinion of the investigator will be allowed to continue receiving treatment (LDE225 and INC424) in an extension phase of this study, until discontinuation reasons are met or an alternative setting to receive study treatment (e.g., in form of another protocol) becomes available.

For details of assessments, refer to [Table 7-1](#) and [Table 7-2](#).

7.1.3 Discontinuation of Study Treatment

Patients may voluntarily discontinue from study treatment for any reason at any time. If a patient decides to discontinue from the study treatment, the investigator must make every effort (e.g., telephone, e-mail, letter) to determine the primary reason for this decision and record this information in the patient's chart and on the appropriate eCRF pages. Patients may be considered withdrawn if they state an intention to withdraw, fail to return for visits, or become lost to follow-up for any other reason.

The investigator should discontinue study treatment for a given patient if he/she believes that continuation would be detrimental to the patient's well-being.

Study treatment must be discontinued under the following circumstances:

- Emergence of the following adverse events:
 - Grade 3 or 4 hemorrhagic event of any kind
 - Grade 3 renal toxicity for ≥ 7 consecutive days
 - Grade 4 renal toxicity
 - Grade 4 non-hematologic toxicity
 - Second occurrence of QTcF > 500 ms (\geq Grade 3) or > 60 ms change from baseline on at least two separate ECGs
 - Patient requires or undergoes splenic irradiation
 - Patient requires or undergoes splenectomy
- Any of the following laboratory abnormalities:
 - Grade 4 anemia for ≥ 7 consecutive days despite PRBC transfusions
 - Febrile neutropenia (Grade ≥ 3) (ANC $< 1.0 \times 10^9/L$, with a single temperature of ≥ 38.3 °C or a sustained temperature of ≥ 38 °C for more than one hour)
 - Grade 3 or 4 serum creatinine
 - Bilirubin $> 10.0 \times ULN$
 - Grade 3 or 4 asymptomatic or symptomatic CK elevation with renal function impairment in which CK and creatinine levels do not return to baseline after interrupting treatment
- Pregnancy

- The following deviations from the prescribed dose regimen for LDE225 and INC424:
 - Interruption of study treatment for > 21 days, regardless of reason, from the intended day of the next scheduled dose. However, if the patient is obtaining clinical benefit in terms of response, the patient may continue treatment at the same or at a reduced dose following discussion between the investigator and Novartis.
 - If after 2 dose reductions and after the treatment has resumed at the lower dose, the same toxicity recurs with the same or worse severity (except for thrombocytopenia, anemia, and neutropenia)
 - If a patient cannot tolerate dose level (-1), which is the lowest acceptable dosing level for this study, except for patients in Cohort 1 who experience thrombocytopenic DLTs and can receive INC424 5mg BID and LDE225 200mg QD.
- Disease Progression
- Use of prohibited treatments (refer to Appendix 1) as determined by Novartis
- Use of another myeloproliferative neoplasm directed therapy
- Any other protocol deviation that results in a significant risk to the patient's safety
- Study is terminated by the Sponsor

Patients who discontinue study treatment should NOT be considered withdrawn from the study. They should return for the assessments indicated in [Table 7-1](#) and [Table 7-2](#). If they fail to return for these assessments for unknown reasons, every effort (e.g. telephone, email, letter) should be made to contact them as specified in [Section 7.1.5](#).

7.1.3.1 Replacement policy

Phase Ib

Dose escalation:

Patients will not be replaced on study. However, enrollment of new patients to a cohort will be considered if there is less than the minimum number of evaluable patients for the DDS.

If a patient is not treated with at least 75% of the planned doses of LDE225 and INC424 in 6 weeks (42 days) (i.e. more than 10 missed doses of LDE225 and more than 20 missed doses of INC424 in 6 weeks), the patient can continue in the study without being evaluable for DDS. Consequently, another patient has to be enrolled into the same dose level in order to reach the required number of patients in the cohort.

Enrollment of new subjects may be considered until at least the minimum number (3) or at most the maximum number (6) of evaluable subjects is achieved within a cohort, see [Section 4.1.1](#).

Dose expansion:

No replacements will be needed, see [Section 4.1.1](#).

Phase II

During Stage 1 and Stage 2 of the Phase II part of the study no replacements will be made.

7.1.4 Withdrawal of Consent

Patients may voluntarily withdraw consent to participate in the study for any reason at any time. Withdrawal of consent occurs only when a patient does not want to participate in the study any longer, and does not want any further visit assessments, and does not want any further study related contact.

Novartis will continue to retain and use all research results that have already been collected for the study evaluation. All biological samples that have already been collected may be retained and analyzed at a later date (or as required by local regulations).

If a patient withdraws consent, the investigator must make every effort (e.g. telephone, e-mail, letter) to determine the primary reason for this decision and record this information.

Study treatment must be discontinued and no further assessments conducted.

Further attempts to contact the patient are not allowed unless safety findings require communication or follow up.

7.1.5 Follow-up for Safety Evaluations

[figure not shown]
All patients, including those who discontinue study treatment and those who refuse to return for an EOT visit, will be contacted for safety evaluations 30 days after the last dose of study treatment. Patients must be followed for the occurrence of Adverse Events, Serious Adverse Events, concomitant medications, antineoplastic therapies used for treating Myelofibrosis disease since discontinuation of study drug, and transfusion use. Patients whose treatment is interrupted or permanently discontinued due to an adverse event, including abnormal laboratory value, must be followed until resolution or stabilization of the event, whichever comes first. See [Table 7-1](#) and [Table 7-2](#) for a complete list of assessments for the 30 day follow up evaluation.

The safety follow-up may be waived if the patient is continuing INC424 and LDE treatment in an alternative setting.

Data collected should be added to the Adverse Events eCRF and the Concomitant Medications eCRF.

7.1.6 Lost to follow-up

For patients whose status is unclear because they fail to appear for study visits without stating an intention to withdraw consent, the investigator should show “due diligence” by contacting the patient, family, or family physician as agreed in the informed consent and by documenting in the source documents the steps taken to contact the patient (e.g. dates of telephone calls, registered letters, etc.). A patient should not be considered lost to follow-up until due diligence has been completed. Patients lost to follow up should be recorded as such on the appropriate Disposition eCRF.

7.2 Assessment types

7.2.1 Efficacy assessments

7.2.1.1 Measurement of spleen length by manual palpation

The response assessment in the Phase Ib part of the study will consist of measuring the spleen length by manual palpation at the end of Week 24 compared to the Week 1 Day 1 measurement. Patients who have a $\geq 50\%$ reduction in spleen size by palpation at the end of Week 24 compared to the measurement at Week 1 Day 1 will be considered responders, otherwise they will be considered non-responders. Spleen length measurements will be taken at Screening, Week 1 Day 1, every 2 weeks until Week 9 Day 1, and every 4 weeks until Week 105 Day 1. Patients in the extension phase will undergo spleen length measurements every 12 weeks from Week 105. All patients will undergo spleen length measurements at the End of Treatment visit.

The edge of the spleen shall be determined by palpation from the left costal margin to the point of greatest splenic protrusion. Palpable spleen length should be measured in centimeters and not in finger breadths.

7.2.1.2 Measurement of spleen volume by MRI/CT

Patients enrolled to the confirmatory MTD level(s) in the Phase Ib part and all patients enrolled in the Phase II part of the study will have MRI/CT of the abdomen performed at Week 1 Day 1, Week 13 Day 1, the end of Week 24, the end of Week 48, and at Week 105 Day 1. Patients in the extension phase will undergo MRI/CT of the abdomen every 24 weeks from Week 105. All patients will undergo MRI/CT of the abdomen at the End of Treatment visit. Patients who have a $\geq 35\%$ spleen volume reduction at the end of Week 24 and Week 48 compared to Week 1 Day 1 will be considered responders, otherwise they will be considered non-responders. See [Table 7-3](#) for the imaging collection plan.

Table 7-3 Spleen volumetric imaging (MRI/CT) collection plan

| Procedure | Collection time points |
|--|--|
| Abdominal MRI of the spleen (or CT if MRI not permitted) Phase Ib- Patients enrolled to the confirmatory MTD level(s) Phase II- All Patients | Week 1 Day 1 |
| | Week 13 Day 1 |
| | At the end of Week 24 and the end of Week 48, and Week 105 Day 1 |
| | Every 24 weeks from Week 105 for patients in the extension phase |
| | End of Treatment |
| Central Reader: MRI/CT scans will be sent to a central lab for analysis | |

MRIs will be performed locally according to the guidelines provided by the designated imaging vendor. The scans from an individual patient will be sent to the designated imaging vendor, who will then provide an independent quantitative assessment of the spleen volume for the study. Spleen volume will be obtained by outlining the circumference of the organ and determining the volume using a validated technique. The MRI will not determine spleen length below the left costal margin, as there are no validated approaches for determining this

measurement. Specific image acquisition parameters and procedures will be provided by the designated imaging vendor.

MRI is the preferred method for obtaining spleen volume data. However, CT scans may be performed if MRI cannot be performed (because of the presence of metal clips in the body, or because of claustrophobia, for example), or if MRI is unavailable to the study site. CT scans will be similarly processed by the designated imaging vendor.

NOTE: Generally, the same method (MRI or CT) should be used for all visits for a given subject unless a new contraindication to the use of MRI (e.g., pacemaker insertion) occurs. Please contact the sponsor if a modality change is required.

7.2.1.3 Change in bone marrow histomorphology

Bone marrow fibrosis will be measured in grades (see [Table 7-4](#)) on biopsy samples obtained for all patients at Week 1 Day 1, Week 25 Day 1, Week 49 Day 1, Week 73 Day 1, and Week 97 Day 1. For patients in the extension phase, biopsy samples will be obtained every 48 weeks from Week 105. Biopsy samples will also be obtained at the End of Treatment visit, if a sample has not already been obtained in the past 24 weeks (see [Table 7-5](#)). Collection, processing and staining of bone marrow aspirations and biopsy samples will be done in accordance with standard procedures at the investigative sites. The bone marrow biopsy and aspirate should be assessed by an experienced hematopathologist using his/her standard examination. Bone marrow fibrosis should be graded using the European consensus grading system ([Tefferi 2006](#)).

[figure not shown]
Table 7-4 Fibrosis grading

| Fibrosis Grade | Description |
|----------------|--|
| 0 | Scattered linear reticulin with no intersections corresponding to normal bone marrow |
| 1 | Loose network of reticulin with many intersections, especially in perivascular areas |
| 2 | Diffuse and dense increase in reticulin with extensive intersections, occasionally with only focal bundles of collagen and/or focal osteosclerosis |
| 3 | Diffuse and dense increase in reticulin with extensive intersections with coarse bundles of collagen, often associated with significant osteosclerosis |

Note: Fibrosis density should be assessed in hematopoietic areas.

The following analyses should be performed:

- Assessment of cellularity.
- 500-cell differential of aspirate, correlated, if possible, with data from appropriate marrow biopsy section. Percentage of pronormoblasts, blasts, normoblasts, myelocytes, metamyelocytes
- Blast percentage, indicating what cellular types are being considered as blast equivalents, and the degree of maturation and dysplastic abnormalities within the neoplastic population should be described.
- Characterization of erythrocyte and megakaryocyte morphology.
- Characterization and gradation of fibrosis within hematopoietic cellular areas.
- Diagnostic interpretation with specific mention of (expected) absence of an infiltrative or granulomatous process

Cytogenetic analysis should include karyotyping and any other tests for which an abnormality has been previously identified in that subject. Any other tests that are considered standard by the Investigator may also be performed.

If samples allow, 3 unstained slides of bone marrow aspirate and half of the bone marrow biopsy sample will be sent to a central lab for central analysis. During or following the study conduct, at the Sponsor’s discretion, a central review of any or all of the bone marrow studies may be conducted by external expert(s) in hematopathology.

Table 7-5 Bone marrow collection plan

| Procedure | Collection time points |
|--|--|
| Bone Marrow biopsy and aspirate for local analysis (Mandatory for all patients) | Week 1 Day 1 |
| | Week 25 Day 1, Week 49 Day 1, Week 73 Day 1, and Week 97 Day 1 |
| | Every 48 weeks in the extension phase from Week 105 |
| | End of Treatment (if not performed in the past 24 weeks) |
| * If a patient is considered to be a non-responder at the end of Week 24 then further bone marrow aspirates and/or biopsies may not be collected To central lab: if samples allow, send 3 unstained slides of bone marrow aspirate and half of bone marrow biopsy sample. | |

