| To assess the efficacy of the co-administration of LDE225 and INC424 on spleen volume reduction as determined by centrally reviewed MRI/CT | Proportion of patients achieving $\geq 35\%$ reduction in spleen volume from baseline as measured by MRI/CT at Week 24 and Week 48 | Refer to Section 10.4 . |
| Secondary | | |
| To assess the effect of the co-administration of LDE225 and INC424 on bone marrow fibrosis by central review and on disease-specific pharmacodynamic biomarkers as a function of the molecular disease characterization of MF | Proportion of patients experiencing improvement in bone marrow fibrosis by at least one grade according to the European consensus on grading bone marrow fibrosis and assessment of cellularity (Thiele 2005) at Week 24 and Week 48 Change in JAK2V617F allele burden from baseline compared to Week 24 and Week 48 Change in cytokine levels from baseline compared to Week 24 and Week 48 | Refer to Section 10.5 . |
| To evaluate the safety of the co-administration of LDE225 and INC424 in patients with MF | AEs, SAEs, changes in hematology and chemistry values, and assessment of physical examinations, vital signs and electrocardiograms | Refer to Section 10.5.1 . |
| To characterize the pharmacokinetics following the co-administration of LDE225 and INC424 | Stage 1: LDE225 and INC424 PK parameters Stage 2: Ctrough of LDE225 and INC424 | Refer to Section 10.5.2 . |

[figure not shown]
[figure not shown]

| Objective | Endpoint | Analysis |
|---|---|---|
| To assess the effect of the co-administration of LDE225 and INC424 on MF-associated symptoms burden | Change from baseline in total symptom score as measured by the modified MFSAF v2.0 at Week 24 and Week 48 Proportion of patients having $\geq 50\%$ reduction in total symptom score from baseline as measured by the modified MFSAF v2.0 at Week 24 and Week 48 Change in EORTC QLQ-C30 scores from baseline compared to Week 24 and Week 48 | Refer to Section 10.5.4 . |

Exploratory

| | | |
|--|--|---|
| Assess the effect of the co-administration of LDE225 and INC424 on Hh pathway target gene expression | Changes from baseline values in key components of the Hh pathway such as Gli1 at Week 24 and Week 48 | Refer to Section 10.6 . |
|--|--|---|

[figure not shown]
4 Study design

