3.6 Secondary analysis

3.6.1 Bone marrow assessment

Bone marrow variables as assessed by aspirate and/or biopsy will be listed. Fibrosis grade assessed by bone marrow histomorphology will be summarized by the collection time points (week 1, week 25 and every 24 weeks thereafter).

The following variables will be listed:

Bone marrow aspirate

[figure not shown]
- Was the specimen adequate for assessment (yes/no),

- Specimen quality: dry tap/hemodiluted/other
- Blast cell (%)

Bone marrow biopsy

- Was the specimen adequate for assessment? (yes/no)
- Percentage of cellularity
- Cellularity: Hypocellular/Normocellular/Hypercellular/Not assessable/Aplastic
- Blast cell (%)
- Bone marrow fibrosis grade

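### The Table 7-5 footnote lets marrow sampling depend on Week 24 response, and the SAP has no denominator or missing-biopsy rule for Week 48 fibrosis improvement

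*Protocol*

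**What the plan says.** **Endpoint.** Protocol Table 3-1 lists as a Phase II secondary endpoint the "Proportion of patients experiencing improvement in bone marrow fibrosis by at least one grade", at Week 24 and Week 48.

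**Collection.** Section 7.2.1.3 grades fibrosis on "biopsy samples obtained for all patients at Week 1 Day 1, Week 25 Day 1, Week 49 Day 1", and again at Weeks 73 and 97. It adds that "Biopsy samples will also be obtained at the End of Treatment visit", unless one was taken in the previous 24 weeks. Table 7-5 heads its row "Bone Marrow biopsy and aspirate for local analysis (Mandatory for all patients". Its footnote then says that if a patient is considered a non-responder at the end of Week 24, "then further bone marrow aspirates and/or biopsies may not be collected".

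**Responder.** The footnote does not define the term. Section 7.2.1.2 (MRI/CT: all Phase II patients and the Phase Ib confirmatory MTD patients) says that patients with at least a 35% "spleen volume reduction at the end of Week 24 and Week 48 compared to Week 1 Day 1 will be considered responders". Section 7.2.1.1 (Phase Ib, palpation) uses at least a 50% "reduction in spleen size by palpation at the end of Week 24".

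**Analysis.** SAP 3.6.1 says "Fibrosis grade assessed by bone marrow histomorphology will be summarized by the collection time points". It does not mention the improvement proportion, its denominator, or biopsies omitted under the footnote.

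**The concern.** In Phase II, response means spleen volume response, which is the primary outcome. The footnote therefore lets the primary outcome decide whether a Week 49 biopsy exists. A Week 48 proportion computed on the biopsies in hand would lean towards spleen responders, yet could be read as the effect in all treated patients. It would also not be comparable with the Week 24 proportion. I take the footnote to act only on samples after the Week 25 biopsy, so Week 24 is not selected in this way.

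Fibrosis carries the disease-modification argument for adding LDE225 (Protocol Sections 2.1 and 2.4), so a selected figure here could mislead about the main reason for the combination.

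**Working it through.** **1. Collection rules side by side.** The table row and the body text of 7.2.1.3 require a Week 49 sample from every patient. The footnote releases Week 24 non-responders. Its wording can be read as an option or as an instruction not to sample, and sites may apply it differently. The End of Treatment biopsy does not close the gap: Week 25 to Week 49 is 49 − 25 = 24 weeks, so a patient biopsied at Week 25 who stops before Week 49 is not due another.

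**2. Which denominator does the plan imply?**
- Towards observed biopsies: Protocol Table 10-2 sends the fibrosis objective to Section 10.5.3.1 (biomarkers). Section 10.5.3.3.1 says that imputation is not usually planned and that the number analysed reflects patients with a valid assessment.
- Towards all patients: SAP 2.2.1 makes the FAS the default set. SAP 3.1 bases percentages on the relevant population or subgroup. SAP 3.5.3 counts Phase II patients with unknown clinical response as non-responders.
- Unresolved: SAP 3.5.3 belongs to the primary analysis, does not mention fibrosis, and also says that no missing values are imputed for efficacy.

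**3. How many patients.** SAP 3.5.2.1.2 gives 20 Phase II patients, and Stage 2 was not started. Protocol 10.8 works with spleen response rates of 40% (no benefit) and 60% (the rate for which power is quoted).
- At 40%: 20 × 0.60 = 12 patients could go unsampled, leaving 8.
- At 60%: 20 × 0.40 = 8 could go unsampled, leaving 12.

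**4. Spread from the denominator alone.** Suppose 8 responders, only those 8 biopsied, and 2 improved. The figure is 2/8 = 25% on observed biopsies and 2/20 = 10% on all patients. With 12 patients unobserved, the full-group result could lie anywhere from 2/20 = 10% to (2 + 12)/20 = 70%. The counts are invented for illustration, but the spread needs no assumption about improvement in non-responders.

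**5. Bias.** The plan states no fibrosis rate to reproduce. Let s be the spleen response share, qR and qN the fibrosis improvement rates in spleen responders and non-responders (assumed), and f the fraction of non-responders still biopsied (assumed).
- True rate = s·qR + (1 − s)·qN
- Observed-biopsy rate = [s·qR + f(1 − s)·qN] / [s + f(1 − s)]
- All patients, missing counted as not improved = s·qR + f(1 − s)·qN

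With s = 0.40, qR = 0.30, qN = 0.10 and f = 0:
- true: 0.4 × 0.30 + 0.6 × 0.10 = 0.18
- observed: 0.12 / 0.40 = 0.30
- missing as not improved: 0.12

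Varying f with the other values fixed:

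| f | Observed biopsies | Missing as not improved | True |
|---|---|---|---|
| 0 | 30% | 12% | 18% |
| 0.25 | 24.5% | 13.5% | 18% |
| 0.5 | 21.4% | 15% | 18% |
| 1 | 18% | 18% | 18% |

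Varying the other inputs at f = 0:
- s = 50% or 60%, qR = 30%, qN = 10%: 30% observed against 20% or 22% true.
- s = 40%, 50%, 60%, qR = 40%, qN = 10%: 40% observed against 22%, 25%, 28% true.
- qR = qN = 30%: 30% observed and 30% true at every s and f.
- s = 40%, qR = 10%, qN = 30%: 10% observed against 22% true, an understatement.

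**The case against.** A reader might infer that the Week 48 result will describe spleen responders only and will overstate improvement. The documents do not support that. It would need every non-responder to go unsampled, although the footnote is not a clear prohibition and Table 7-5 and 7.2.1.3 ask for a sample from everyone. It would also need better fibrosis improvement in spleen responders, and the documents give no rate for either group. Nor does the SAP commit to observed cases: its general rules can be read as an all-patient analysis, in which case any bias runs downward. All of this stands, and it limits the point to a conditional one.

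Two further limits stand. The footnote's asterisk has no visible anchor in the extracted table, and it does not say spleen; that meaning comes from 7.2.1.1 and 7.2.1.2. Non-response is also not the only cause of missing grades: 14 of 50 treated patients had discontinued by February 2015 (Amendment 2 rationale), and SAP 3.6.1 itself records inadequate specimens and dry taps.

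The stakes can also be called modest: 20 single-arm patients, a descriptive endpoint, and no decision rule that uses it. That limits the consequence but does not remove it. With so few patients, losing 8 to 12 biopsies by outcome leaves little to interpret unless the rule is stated.

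**Conclusion.** The point holds in conditional form. The footnote contradicts the table it belongs to and the text above it. Where it is used, Week 48 fibrosis data are missing according to the primary outcome, and the SAP does not say how such patients count. The protocol's route through the biomarker section points to an observed-biopsy figure, which would be enriched for spleen responders.

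Such a figure may overstate improvement. At the extreme of no non-responder sampled, the excess is 8 to 12 points for assumed improvement rates of 30% against 10%, and 12 to 18 points for 40% against 10%, over spleen response of 40% to 60%. A positive association is plausible, since Section 1.4.2.2.3 describes extramedullary hematopoiesis as a direct consequence of marrow fibrosis, but no figure in the documents establishes it. The excess is zero if all are sampled or the two outcomes are unrelated, and it changes sign if the association is negative. The actual number of Phase II responders is not stated, so the number affected is unknown.

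**What to change.** 1. **Protocol.** Reconcile the Table 7-5 footnote with the mandatory heading of the same table and with the all-patient schedule in 7.2.1.3. State which definition of non-responder it uses and which visits it covers.
2. **SAP 3.6.1, main figure.** Define the Week 48 improvement proportion on all Phase II FAS patients with a baseline grade. Count patients without a Week 48 grade as not improved, whatever the reason. State that this is a conservative lower bound. It follows the treatment of unknown response in SAP 3.5.3.
3. **SAP 3.6.1, companion figure.** Show the observed-biopsy proportion beside it, labelled as such and split by Week 24 spleen response. Do not label the total as a result in spleen responders, because some non-responders may have been biopsied.
4. **Counts.** In each Week 24 response group, give the number biopsied at Week 49 and the number not sampled under the footnote.

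The analysis part costs one SAP paragraph and needs no extra biopsies. The downside is a less favourable Week 48 figure, which understates the truth if any unsampled patient improved (12% against 18% in the illustration). That is why it should be called a lower bound and shown with the companion figure.
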